In all 3 groups, daily adherence, cravings and sleep measures will be compared within and across groups. During the Pre-Study Screening, we will explain the study to the subject and ask that she completes an Intake Questionnaire to better understand any previous experiences she may have had with opioid treatment or detox programs. We will also perform urine and blood testing to assure all entry criteria are fulfilled. Once consent is obtained, we will initiate a Suboxone or Subutex dose reduction schedule similar to the one shown in Table 1. To ascertain the impact of a dose change, all subjects will complete 4 daily VAS questionnaires similar to those used by Dunn et al. ⁴⁶ to assess withdrawal, cravings, sleep duration and sleep quality. The scales will range from a score of 0-10 for each question. Subjects that wish to be contacted via text will be sent a daily text with a link to the REDCap website where they can complete the VAS

questionnaire electronically throughout the dose reduction process. Subjects that are unable to receive daily text messages will be provided hard copies of the VAS questionnaire and instructed to return the completed forms to research staff at their next appointment. Clinic visits will occur weekly or biweekly at which time we will monitor plasma BUP+M, neurotransmitter and cotinine concentrations and perform a comprehensive urinary toxicology test. Additionally, at each clinic visit we will administer the Weekly Follow-up and Weekly Smoking and Alcohol Use questionnaires. We will also collect any completed VAS forms, if applicable, and perform COWS and Subjective Opioid Withdrawal Scale (SOWS) scores to assess current clinical and subjective symptoms of withdrawal and satiety. All subjects will receive psychosocial support, as needed. The timing of the subject's scheduled visits will be determined by their healthcare provider.

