Since our focus is to assess whether the magnitude of the dose change, frequency of dose change and dosing frequency impact adherence during reduction, this pharmacodynamic study will be completed when the subjects are off BUP entirely or on the lowest tolerable dose. However, we will continue to see the subjects weekly or biweekly, monitor their adherence and continue to provide counseling sessions, as needed, until the 6-week postpartum visit. We will also evaluate peripheral blood mononuclear cells (PBMCs) as a surrogate marker of metabolic enzymes and transporters. The expression of drug metabolizing enzymes and transporters in the PBMCs will be correlated with the plasma concentrations of BUP and its major metabolites. Two maternal blood samples will be drawn for PBMC analysis; one during pregnancy and one in postpartum. The first sample will be drawn during the Pre-Study Screening; however, if this is not possible, it may be drawn at any time during pregnancy. The second sample will be drawn at 4-6 weeks postpartum, but as close as possible to the 6-week postpartum visit.

For subjects not enrolled in specific aim 3a or 3b, we will collect a cord blood sample at the time of delivery as well as maternal and newborn hair within 3 days of delivery, when possible. An additional cord blood sample (10 mL) will be drawn for genetic studies related to metabolizing enzymes, if the mother consents. The minimal amount of hair needed is 20 mg but we will ask for 100 mg which is still a very small amount. Hair will be removed from the mothers and baby's head (if consent is granted). Mother will decide where the hair will

be removed from her and her baby. The collection of these samples will be described in full detail during the consent process.

Note: Subjects that consent to participate in specific aims 3 (Parts 1 or 2) will already have the cord blood and hair samples collected as part of that specific aim. The collection of these biological samples only applies to those subjects not already enrolled in specific aim 3.

Table 1.

Dose Reduction Schedules if Start Dose is 16 mg Daily			
Group	Frequency	Magnitude	Dosing
Strategy	Reduce dose by 2 mg weekly then biweekly, repeat till dose=0 or at the lowest possible dose	Reduce dose by 1 and then 2 mg weekly, repeat above till dose=0 or at the lowest possible dose	May elect either the Frequency or Magnitude dose reduction schedule.
Dosing Frequency	QID or TID	QID or TID	BID
Dose			

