Week 1	16	16	Refer to the appropriate dose schedule in the Frequency or Magnitude columns
Week 2	14	15	
Week 3	14	13	
Week 4	12	12	
Week 5	10	10	
Week 6	10	9	
Week 7	8	7	
Week 8	6	6	
Week 9	6	4	
Week 10	4	3	
Week 11	2	1	
Week 12	2	0	
Week 13	0	0	

e) Statistics

The outcome(s) of interest are the pharmacodynamic endpoints that reflect the acclimatization of the mu receptors and opioid-affected brain functions. Each subject in a group will undergo alternating treatments to minimize any between subject differences that would impact the response to the decrease in dose. In this study, we will rely on scores from the self-administered VAS questionnaires. We will determine both an average and highest value for each of the VAS questionnaires weekly. The average values over the 7 days of

that given dose from the VAS questionnaires will be combined to create a single score for each week. A similar approach will be taken for the highest rather than average values. Based on the study of Dunn et al ^{46,47}, the mean value for the withdrawal VAS questionnaire (scale 1-10) in non-pregnant subjects was 30 with a standard deviation of ~25. These values are estimates since graphs were provided but not tabular data. A difference of 25% in the VAS combined scores between any of the comparisons would seem clinically meaningful. Thus, a sample size of 10 in each group is sufficient to detect a difference in VAS scores between any of the comparison groups. The comparisons in the Frequency group will be VAS scores between the 1 vs 2 week reductions. The comparisons in the Magnitude group would be VAS scores between the 1 and 2 mg reductions. The comparison in the Dose group will be a comparison of the VAS scores during the 1 mg and 2 mg reductions. Also, VAS scores in the Dose group will be compared to the VAS scores in the Magnitude group both at the 1 and 2 mg reductions. The change in mu receptor sensitivity will be determined by comparing the BUP+M

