concentration each week to the subjects VAS scores on craving and withdrawal symptoms. In women who supplement their weekly BUP regimen with other opioids detected at the weekly clinic visits their VAS questionnaires on withdrawal and craving will be scored as 100. Assay Methods: BUP+M will be assayed using UPLC-MS-MS. We have developed and validated this assay and with the new TQS system the LOQ is 15 ng/ml in plasma. BUP in hair and other tissues will be measured by modification of this method and incorporating elements of methods reported in the literature ^{30,31,33}. Cotinine will be measured by minor modification of the published method ⁵⁵.

Anticipated sum of mean VAS scores	Percent Reduction in VAS scores	Sample Size
120	0.15	25
120	0.20	15
120	0.25	10
120	0.30	7

D. Study Procedures

D.1 Screening for Eligibility

The inclusion/exclusion criteria will be reviewed with the patient's chart. Any woman who appears to be eligible will be informed about the study. If a patient appears to meet the criteria for enrollment and expresses interest in the study, she will be told about the study and asked to sign the informed consent form. She will be asked to sign a medical records

release so that the medical records may be obtained. A copy of the signed consent form will be provided to the patient.

D.1.i. Gestational Age Determination

We will use the criteria recommended by the American Congress of Obstetricians and Gynecologists (ACOG).

D.2 Informed Consent Procedures and Documentation

Written informed consent will be obtained before entry into the trial. Full disclosure of the nature and potential risks of participating in the trial will be made. Women who are not fluent in English will be enrolled by a person fluent in their language and both verbal and written informed consent obtained in that language; if such are not available, they will not be included.

D.3 Specimen Collection

Per standard research procedures for Labor and Delivery samples, Magee Womens Hospital employs staff as part of the Obstetric Specimen Procurement Unit (OSPU), which is responsible for the collection of research study samples on the Labor and Delivery unit. Labor and Delivery samples will only be collected if possible. There is a 3-day window for collection of hair samples. Maternal and infant samples will be collected as shown in Table 2.

D.4 Specimen Analysis and Collection of Negative Control Samples

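### The VAS is collected on 0-10, but the planning figures (mean 30, SD about 25, sum 120) and the assigned score of 100 do not fit that scale, and the plan does not say which weeks of a removed woman are analysed

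*Combined protocol and SAP*

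**What the plan says.** All references are to the combined protocol and SAP.

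- **Collection.** Section d) Study Design says that "all subjects will complete 4 daily VAS questionnaires", covering withdrawal, craving and two aspects of sleep, and that "The scales will range from a score of 0-10 for each question".
- **Weekly outcome.** Section e) Statistics averages each questionnaire over the seven days at a dose. These averages "from the VAS questionnaires will be combined to create a single score for each week".
- **Planning figures.** The same section gives the mean for "the withdrawal VAS questionnaire (scale 1-10) in non-pregnant subjects was 30", with an SD of about 25, both read from published graphs. The sample-size table lists the "Anticipated sum of mean VAS scores" as 120 and gives 10 per group for a 25% difference.
- **Assigned score.** For women found at weekly visits to be supplementing with other opioids, "their VAS questionnaires on withdrawal and craving will be scored as 100".
- **Removal.** Section G, Subject Removal Criteria, drops and replaces a woman if another opioid is found in her urine at any time during the study. Neither this section nor section e) refers to the other.
- **Schedules (Table 1).** Magnitude: "Reduce dose by 1 and then 2 mg weekly, repeat above till dose=0 or at the lowest possible dose". Frequency: "Reduce dose by 2 mg weekly then biweekly, repeat till dose=0 or at the lowest possible dose".

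**The concern.** A 0-10 item cannot average 30 or take the value 100. The mean and SD are planning inputs, but the score of 100 is an operating rule applied to collected data, so whoever programs the weekly score must guess between 100 and 10. With 10 women per group, that guess could decide a comparison. The same withdrawal and craving scores are also set against weekly buprenorphine and metabolite concentrations to answer the third primary question, on mu receptor sensitivity.

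The second gap is about which data count. Section e) scores the questionnaires of a woman with other opioids detected, and section G removes her on the same kind of finding. The plan does not say whether her positive week, her earlier weeks, or none of her weeks are analysed.

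**Working it through.** **1. The plan's own sample sizes.** Inputs from section e): sum 120, SD 25, differences of 15, 20, 25 and 30%, that is 18, 24, 30 and 36 points. The test, alpha and power are not stated. A two-sample t test at one-sided alpha 0.05 with 80% power gives 25, 15, 10 and 7 per group, matching every row. Some paired settings come close (paired t, two-sided, 90% power: 23, 14, 10, 8), so the settings are inferred.

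**2. Does rescaling change N?** Divide everything by 10: sum 12, SD 2.5, differences 1.8, 2.4, 3.0 and 3.6. The standardised difference is the same (30/25 = 3.0/2.5 = 1.2), and so is N: 25, 15, 10, 7.

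**3. Bounds on 0-10, taking one item per questionnaire.**

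- Largest sum: 4 × 10 = 40. The planned 120 is 120/40 = 3 times that.
- Target: 0.25 × 120 = 30 points, or 30/40 = 75% of the maximum.
- Largest SD of one item: half the range, 5 (as a sample SD with n = 10, 5 × √(10/9) = 5.27). The plan uses about 25.
- On 0-100 the figures fit together: 4 × 30 = 120, and 100 is the item maximum.

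**4. Effect of one positive week on 0-10 data.** Assume the planning figures divided by 10: each item averages 3, a typical week is 4 × 3 = 12, and the target is 0.25 × 12 = 3.0. Assume the two sleep items stay at 3.

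- 100 entered literally: 100 + 100 + 3 + 3 = 206, an increase of 206 − 12 = 194.
- Scale maximum entered: 10 + 10 + 3 + 3 = 26, an increase of 26 − 12 = 14.

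Average each woman's k weeks of a step type, then average over 10 women. The shift is 194/(10k) or 14/(10k). Counts of k come from Table 1 (16 mg start), classing each dose by the size of the step to it or the time it is held, including the first week at dose 0, and with the woman contributing every week. Section d) expects slower tapering to be better tolerated, so the gentler steps (1 mg, two-week) are taken as the lower-scoring ones.

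| Step | Expected score | k | Literal 100 | Scored as 10 |
|---|---|---|---|---|
| 1 mg | lower | 6 | 3.23 | 0.23 |
| Two-week | lower | 8 | 2.43 | 0.18 |
| 2 mg | higher | 5 | 3.88 | 0.28 |
| One-week | higher | 4 | 4.85 | 0.35 |

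Excluding the dose-0 week leaves 5 weeks for the 1 mg step (194/50 = 3.88) and 3 for the one-week step (194/30 = 6.47; 14/30 = 0.47).

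In the lower-scoring step, a literal 100 turns a true difference of 3.0 into 3.0 − 3.23 = −0.2 (1 mg) or 3.0 − 2.43 = +0.6 (two-week). In the higher-scoring step it inflates the difference.

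**5. Effect of removal.** If the positive week is not analysed, the shift is 0. If the woman is removed early, her weeks are kept and her replacement is also counted, it is 194/(11k) with a smaller k. For example, a positive test at week 4 of the Magnitude schedule leaves two 1 mg weeks: 194/(11 × 2) = 8.8.

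**The case against.** The strongest reply is that this is a labelling slip. The planning figures agree with each other on 0-100, 100 plainly means the worst possible score, and an experienced analyst would enter 10 on a 0-10 form. On that reading the effect is small and N does not move. This stands as far as it goes, but the plan states no conversion and the rule as written gives a number, not the scale maximum.

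A second reply is that section d) gives 0-10 for each question, so a questionnaire with several questions could total more than 10. The instrument is not in the documents, so the maximum of 40 is an inference. It is the more natural one, because section e) labels the withdrawal questionnaire itself as 1-10, and a mean of 30 contradicts that label however many questions there are. The lower bounds (0 and 1) also disagree.

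Three stronger readings are tempting, and the documents do not support them.

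- *One positive week clearly reverses the result.* In the steps expected to score lower, the remaining difference is near zero or still positive on the Table 1 counts. The larger shifts there belong to the other steps, where they inflate the difference. Only by excluding the dose-0 week does the 1 mg shift (3.9) clearly exceed the target.
- *The scale error makes the sample size wrong or costs a known amount of power.* Rescaling leaves N unchanged. The plan gives neither the test, its sidedness nor the SD of a within-woman difference, so no power figure can be attached to this point.
- *Sections e) and G contradict each other.* Both can operate: a week can be scored and the woman then removed. What is missing is how they combine. No maximum shift is given for early removal, since it depends on that missing rule, and a woman removed during her first step has no comparison step and so no within-woman difference.

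**Conclusion.** The point holds as an inconsistency of scale plus an unreconciled data rule, and it should be fixed before scoring. The inconsistency rests on the text alone; the statement that 30, 25, 120 and 100 cannot occur rests on one 0-10 item per questionnaire.

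The consequence is conditional. Read as the scale maximum, the assigned score moves the mean difference by about 0.2 to 0.35 points, 6 to 12% of the 3.0-point target, when the woman contributes every week. Entered literally and analysed, one week in one of 10 women can cancel or nearly cancel the target difference. The literal figures need all of the following: 0-10 data, 100 entered as written, the positive week kept, planning figures divided by 10, equal weighting of weeks and the Table 1 counts.

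Unchanged N is not support for N = 10. Reproducing the table means applying an SD given for one questionnaire to a sum of four, which is a separate matter.

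**What to change.** 1. Use one scale for collection, planning and the assigned score.
   - If 0-10 is kept, replace the score of 100 with the scale maximum of 10 and correct the 1-10 label. Restate the planning figures as mean 3, SD 2.5 and sum 12, on condition that the sponsor confirms the cited study used 0-100; state the conversion.
   - If 0-100 was meant, correct section d) and the questionnaire instead, and say how any 0-10 responses already collected will be converted.
2. Reconcile sections e) and G for analysis purposes. State which weeks of a removed woman enter the analysis (those before the positive test, the positive week, or none), whether the assigned score applies to them, and whether she and her replacement both count. This does not require changing who is removed.

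If 0-10 is kept, the cost is wording in the Statistics and Subject Removal sections plus scoring code, with no change to visits or questionnaires. Moving to 0-100 would also change the instrument.

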5-24-2021

Pharmacologically-based Strategies for Opioid Substitution Therapy During Pregnancy

PRO18070495 / STUDY19100128

NCT03831113

Protocol version 1.8

The Eunice Kennedy Shriver National Institute of Child Health and Human Development (NICHD)

Principal Investigator:

[name]
Magee-Womens Hospital
[name]
[name]

Specific Aim 4

Specific Aim 4 compares dose reduction strategies for Suboxone or Subutex in pregnancy that are based on the pharmacodynamic and pharmacokinetic characteristics of BUP.

a) Primary Research Questions

1. Is adherence during dose reduction influenced by the magnitude or frequency of a given dose reduction?
2. Is adherence during dose reduction influenced by dosing frequency?
3. Does mu receptor sensitivity change during dose reduction?

b) Eligibility Criteria

Inclusion Criteria – must meet all of the following:

1. On a stable BID, TID or QID dosing regimen of BUP for at least 2 weeks as part of an established medication- assisted treatment (MAT) program.
2. Willingness to undergo supervised dose reduction
3. Subjects on BID, TID or QID dosing, willing to be assigned to the Magnitude, Frequency, or Dosing group, depending on their current dosing
4. Single gestation between 14-30 weeks at the initiation of dose reduction
5. On a BUP dose between 6- 24 mg daily (lower doses will not provide sufficient data points)
6. Willingness to have urine samples tested for drugs of abuse and blood samples tested for BUP+M concentrations during the Medical Supervised Withdrawal (MSW) clinic appointments
7. Willingness to attend weekly or biweekly MSW clinic appointments and to have daily contact via text messaging to complete daily logs of sleep quality, withdrawal symptoms and symptoms of craving. Subjects may consent to receiving daily text messages with a link to a REDCap where they can complete the daily questionnaires electronically. Alternatively, they may complete hard copies of the questionnaires and return them during their weekly clinic visits.
8. Willingness to attend psychosocial support meetings, as needed.

Exclusion criteria – cannot meet any of the following:

1. Current use of cocaine, heroin, benzodiazepines, barbiturates, phencyclidine (PCP), or opioids other than BUP
2. Currently taking more than two mental health medications

3. Active moderately severe depression (PHQ-9 score ≥ 15 or suicidal ideation)
4. Current incarceration

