- A PHQ-9 score of ≥ 15 represents moderately severe depression. Subjects with a score of ≥ 15 at the Pre-Study Screening will be excluded from participating in the study and will be referred to a mental health provider.

Note: Question 9 on the PHQ-9 is a single screening question on suicide risk. If a subject answers yes to question 9, they are ineligible to continue with the study and will be immediately referred to a mental health provider for further assessment.

Once recruited subjects are on a stable dose of Suboxone or Subutex for 2 or more weeks, we will initiate one of three dose reduction strategies. We will compare tolerance in the same person to an alternating 1 mg vs 2 mg weekly reduction (Magnitude group, n=10). In a second group (Frequency group, n=10) we will compare tolerance in the same person to an alternating 2 mg reduction occurring weekly vs bi-weekly. All subjects in the Magnitude and Frequency groups will be on TID or QID dosing. In a third group (Dosing Group, n=10) we will compare tolerance to either the Magnitude or Frequency reduction schedule in women who are on a BID dosing regimen. The comparisons in these three groups will address those fundamental questions required for development of a rational dose reduction strategy. Each of these strategies addresses a specific question about maternal accommodation to the specified dose change. The dose reduction magnitude of 1 mg vs 2 mg and the frequency of reduction of weekly vs bi-weekly selected are based in large part on the work of Sigmon et al.⁴⁷ but larger and more frequent reductions could be considered. We chose this modest reduction strategy as we were concerned that more aggressive changes could lead to subject withdrawal and dissatisfaction. In the study of Sigmon et al.⁴⁷, only 50% of participants were opioid abstinent with the 4-week taper (i.e. 1.75 mg per week). We believe a slower taper regimen could improve upon this outcome. Table 1 provides an example of the dose reduction strategy assuming, as an example, a starting dose of 16 mg daily. Subjects on TID or QID dosing will be assigned to either the Frequency or Magnitude groups based on their current dosing. Subjects on BID dosing will be assigned to the Dosing group.

- Subjects assigned to the Frequency group will have dose reductions of 2 mg on alternating intervals of 1 and 2 weeks.
- Subjects assigned to the Magnitude group will have alternating reductions of 1 then 2 mg every week.

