Recruitment of subjects for specific aim 4, dose reduction may prove challenging since we have not offered this option previously at Magee; however, we performed a survey recently of potential candidates for dose reduction and detoxification and the response was very encouraging. Of 40 women asked if they would consider dose reduction or detoxification, more than 50% said they would be interested. Recruitment for specific Aim 1 may be challenging because the subject will need to be willing to allow withdrawal to occur in addition to spending time in the CRC. Time in the CRC has been an ongoing challenge to recruitment in all OPRU studies. Given that all the MAT clinic staff have been involved with our BUP research in the past and 2 BUP writers are supported by this grant, I am confident that we can recruit sufficient subjects to complete these aims.

F. Potential Problems & Alternative Strategies

For all specific aims, recruitment must be considered. Although this is unlikely to be problematic given our large population, it may be an issue. If recruitment is slower than required to achieve our goals, we will approach other research-oriented centers with a large opioid using population to assist in recruitment.

For specific aim 4, possible problems include high drug withdrawal and craving on the lowest dose reduction and a high dropout rate. The possibility that even the lowest dose reduction will lead to unacceptable rates of dropout and study withdrawal rates is not likely given the reasonable dose reduction rates reported by others with dose reductions much greater than those proposed. If this does indeed happen then we would target an even slower rate of reduction.

G. Subject Removal Criteria

For specific aim 4, if heroin, cocaine, benzodiazepines, barbiturates, phencyclidine (PCP), or opioids other than BUP are detected in the urine during the pre-study screening or at any time during the study, or if the urine drug screen results from the MAT clinic are positive at any time during her dose reduction, she will be dropped from the study and replaced. Subjects who do not return their residual drug on more than 3 occasions will be withdrawn from the study.

H. Clinical Data Management

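### The plan both removes and worst-scores a woman with another opioid detected during the taper, without saying whether her weeks are analysed

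*Combined protocol and SAP*

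**What the plan says.** All references are to the combined protocol and SAP, Specific Aim 4.

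- **G. Subject Removal Criteria.** If another opioid or one of several listed drugs is found in urine at screening or at any time in the study, or the treatment clinic's drug screen is positive during dose reduction, "she will be dropped from the study and replaced". A positive at screening is an eligibility failure and is not at issue here.
- **e) Statistics.** For women with other opioids detected at the weekly visits, "their VAS questionnaires on withdrawal and craving will be scored as 100". The two sleep scales are not rescored.
- **d) Study Design.** Urine toxicology is done at each clinic visit, so one result can trigger both rules. Also: "In all 3 groups, daily adherence, cravings and sleep measures will be compared within and across groups".
- **a) Primary Research Questions.** The first question is "Is adherence during dose reduction influenced by the magnitude or frequency of a given dose reduction"; the second asks the same about dosing frequency.
- **e) Statistics, comparisons.** Besides the within-woman contrasts, "VAS scores in the Dose group will be compared to the VAS scores in the Magnitude group".
- **d) Study Design, rationale.** In a cited taper study "only 50% of participants were opioid abstinent with the 4-week taper (i.e. 1.75 mg per week" and the sponsor adds "We believe a slower taper regimen could improve upon this outcome".
- **F. Potential Problems & Alternative Strategies.** On unacceptable dropout: "If this does indeed happen then we would target an even slower rate of reduction".

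Neither section G nor the Statistics section refers to the other. No text defines an analysis set, gives precedence, or says what happens to the weeks of a removed woman.

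**The concern.** A positive urine for another opioid is the clearest sign that a reduction step has failed. The scoring rule treats it as a worst outcome to be counted. The removal rule, on the natural reading of replacement in a group fixed at ten, takes the woman out and puts another in her place. Two analysts could follow the plan in good faith and produce different data sets.

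The asymmetry makes this more than a missing detail. A woman who cannot tolerate a step but has a clean urine stays in, returns to her last tolerated dose, and her VAS records the intolerance. A woman whose step fails through opioid use may leave the comparison. Removal then depends on the outcome, in a study that asks about adherence and tolerance. Stopping the taper after a positive urine is clinically defensible; the statistical question is whether her weeks still count.

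**Working it through.** **1. The plan's own target.** The Statistics section takes a 25% difference in a combined score of 120, so 0.25 × 120 = 30 points, with 10 women per group. With SD 25, a two-sample t-test at one-sided 5% and 80% power returns 25, 15, 10 and 7, matching all four rows of the sample size table. The plan does not state test, sidedness or power; these are the settings that reproduce it. The figure of 10 is not in dispute here.

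**2. How often the rules collide.** The removal rate is not given; I assume 10% to 50%. The 50% non-abstinence in the cited taper is only a rough upper anchor. That taper ran at 1.75 mg per week, against (1 + 2)/2 = 1.5 for the Magnitude schedule and 4 mg per 3 weeks = 1.33 for the Frequency schedule.

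| Assumed rate | At least one of 30 starters | Starters for 30 retained | Replaced |
|---|---|---|---|
| 10% | 1 − 0.9^30 = 96% | 30/0.9 = 33 | 3 |
| 30% | 1 − 0.7^30 > 99.9% | 30/0.7 = 43 | 13 |
| 50% | 1 − 0.5^30 > 99.9% | 30/0.5 = 60 | 30 |

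(The first column treats every removal as an opioid positive; section G also covers other drugs.)

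**3. What the retained ten cannot show.** At a true 50%, ten retained women show 0/10 relapses (exact 95% CI 0 to 31%), while the 20 who started show 10/20 (27% to 73%).

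**4. What one worst-scored week does.** Assumptions: a 0-100 scale, four scales with mean 30, and weeks averaged within woman and condition. The design section gives 0-10; with the maximum rescaled to match, the percentages below are unchanged.

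- Positive week: 100 + 100 + 30 + 30 = 260, which is 140 above 120.
- With k weeks in that condition, one woman in ten shifts the contrast by 140/(10k).
- Table 1 Magnitude schedule from 16 mg: six 1 mg and five 2 mg steps. k = 6 gives 2.3, k = 5 gives 2.8, k = 1 gives 14. Against 30 points: 8%, 9% and 47%.
- If she would have scored 60 on both scales anyway, the excess is 200 − 120 = 80, and the shift runs from 80/60 = 1.3 (4%) to 80/10 = 8 (27%).
- If she is excluded, her positive week contributes nothing.

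The order is fixed, 1 mg then 2 mg. A woman positive at step one has no 2 mg week and so no pair, so k = 1 in a paired analysis can arise only at step two.

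**5. Why keeping only complete pairs is not a sound repair.** Assume no true effect, an equal weekly hazard h at both step sizes, 11 steps, and the taper ending at the first positive. Then h = 1 − (1 − p)^(1/11), or 0.0095, 0.0319 and 0.0611 for p = 10%, 30% and 50%. Among women who pass step one, the expected shift in 2 mg minus 1 mg is the sum over s = 2 to 11 of ±(1 − h)^(s−2) × h × 140/k, where k is s/2 for even s (2 mg, plus sign) and (s + 1)/2 for odd s (1 mg, minus sign).

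| p | Step 2 (140h) | Steps 3-11, net | Total | Share of 30 |
|---|---|---|---|---|
| 10% | 1.33 | −0.22 | 1.1 | 4% |
| 30% | 4.47 | −0.72 | 3.7 | 12% |
| 50% | 8.55 | −1.36 | 7.2 | 24% |

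With the 80-point excess the totals are 0.6, 2.1 and 4.1. So dropping step-one failures while worst-scoring step-two failures makes 2 mg look worse when it is not. Pooled over all weeks at risk, the expected excess is 140h per week in both conditions, and the difference is zero.

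**The case against.** The strongest reply is that there is no contradiction. Section G governs participation and the Statistics section governs scoring; scoring the positive week and then removing and replacing her satisfies both. The scoring rule would have almost no use if such women were excluded, which favours that reading. This stands: a reader might infer that exclusion is planned, but no text says collected data are discarded. What remains is that the plan does not state the reconciled reading.

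A reader might also infer that the trial will report an inflated abstinence rate. The documents do not support that. The Statistics section relies on VAS scores, no abstinence or relapse rate is a planned endpoint, adherence has no urine-based definition, and the 50% figure is background for the choice of taper speed. The 0/10 versus 10/20 contrast shows only what the retained women cannot tell us.

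The removal rates are assumed. The cited study's handling of dropouts is not visible, women here may step back a dose and use ancillary medication, and section G covers more than opioids, so 50% is not a proven ceiling. The near-certain collision says nothing about harm. The 47% shift is a corner case. Dosing versus Magnitude is already non-randomised, since assignment follows current dosing, and removal adds bias only if rates differ.

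Finally, data are entered in a database and section F anticipates dropout, so counts could be reported without an amendment. True, but nothing commits the sponsor to a count over all women who started.

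**Conclusion.** The concern holds as an unresolved rule with an outcome-dependent removal on its natural reading. If removed women are not analysed, absolute tolerance and adherence will look better than they were, and Dosing versus Magnitude can be biased if removal rates differ between groups. For the 1 versus 2 mg and 1 versus 2 week contrasts, the direction of any bias is not established.

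The choice of rule can move a within-woman contrast by 1.3 to 14 points per affected woman (4% to 47% of the target), depending on the assumed scale, her counterfactual score and how many weeks she contributed. How many women are affected rests on an assumed 10% to 50% removal rate. This is a cheap improvement rather than a fatal flaw; confidence is medium, because the reconciled reading may be what the sponsor intends.

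**What to change.** 1. Amend section G and cross-refer it to the Statistics section: a positive urine after the taper starts may end the reduction, and she may be replaced, but all her data up to and including the positive week stay in the analysis.
2. Apply the worst-score rule at the maximum of the scale in use. It covers other opioids only, so state how weeks positive for the other listed drugs are handled; analysing them as observed is the simplest choice.
3. Analyse at the week level over all women who started a reduction, for example with a mixed model with a woman effect, including women who contributed only one condition. Do not restrict to complete pairs. A large woman effect pulls the model back towards within-woman information, so read it beside the table in item 5.
4. Add a sensitivity analysis with positive weeks as observed.
5. Report the number and timing of positives and early stops by group and reduction step, per week at risk, over all starters. Use that rate to decide on the slower taper in section F.

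The cost is amendment wording, one table and one sensitivity analysis on data already collected, with no added visits. Reported tolerance will be less favourable.
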